## LIST OF ABBREVIATIONS

*(examples of some commonly used abbreviations, include any used in protocol)*

AE	Adverse Event
ANC	Absolute neutrophil count
BUN	Blood urea nitrogen
BRS	Biospecimen Repository Service
CBC	Complete blood count
CINJOG	Cancer Institute of New Jersey Oncology Group
CT	computer tomography
CR	Complete response
CRF	Case Report Form
CTCAE	Common Terminology Criteria for Adverse Events
DSMP	Data Safety Monitoring Plan
ECG	Electrocardiogram
FDA	Food and Drug Administration
HHS	Department of Health and Human Services
IRB	Institutional Review Board
kg	kilograms
mL	milliliters
mcg/µg	Micrograms
MRI	Magnetic Resonance Imaging
NCI	National Cancer Institute
NIH	National Institutes of Health
OHRS	Office of Human Research Services
OHRP	Office of Human Research Protection
PBMC	Peripheral blood mononuclear cells
PD	Progressive disease
PET	Positron Emission Tomography
PHI	Protected health information
PI	Principal Investigator
PR	Partial response
RWJUH	Robert Wood Johnson University Hospital
SAE	Serious adverse event
SD	Stable disease
sCr	Serum creatinine
SGOT	Serum glutamic oxaloacetic transaminase
SGPT	Serum glutamic pyruvic transaminase
ULN	Upper limit of normal

### 1. Purpose/Specific Objectives

The purpose of this protocol is to serve as a pilot study for neoadjuvant cetuximab in potentially resectable, advanced squamous cell carcinoma. The primary hypothesis is that cetuximab used in

the neoadjuvant setting for locally advanced squamous cell carcinomas is both safe and well tolerated and that its use may enhance the treatment of advanced cases of SCCS when delivered preoperatively. The overall treatment strategy expressed in the protocol is to treat locally advanced/unresectable squamous cell carcinomas with 8 weeks of neoadjuvant cetuximab, and monitor patients for disease response, adverse events, and overall safety. Potentially, patients may be able to go on to surgical resection if adequate disease response is achieved. The hope is that the data derived from this study will lead to a large randomized trial testing the efficacy of this approach in this disease, which has few available treatment options.

### **1.1 Primary Objective(s)**

The co-primary endpoints are to

- a) assess the response rate of cetuximab by RECIST criteria in patients with advanced SCCS and, b) to assess whether neoadjuvant cetuximab given in this patient population is both safe and feasible.

### **1.2 Secondary Objective(s)**

1.2.1 To measure the progression free and overall survival of patients with advanced SCCS who receive neoadjuvant cetuximab.

1.2.3 To determine the conversion to resectability of patients treated with neoadjuvant cetuximab and capture changes in reconstructive options rendered possible by neoadjuvant treatment.

1.2.3 Molecular correlates. All patients must have a biopsy of the locoregional disease (primary site or neck lymph nodes), and of the skin prior to therapy. Patients will also have tissue harvested at surgery that will undergo molecular analysis, or a second post treatment biopsy if surgery is not feasible. Our goals in the molecular analysis are to explore the following possibilities:

- Analyze the relationship of known DNA mutations in tumor per the FoundationOneTM genomic profile, and correlate to clinical endpoints such as clinical benefit and conversion to resectability to discover potential markers of response and/or resistance.
- Measure the downstream activation of signaling pathways without a known driver, including the EGFR pathway.
- Determine if tumor shrinkage with cetuximab is associated with increased apoptosis as evidenced by activated caspase-3, in pre- and post- treatment tumor tissues.
- Determine whether cetuximab results in increased ADCC in post-, compared with pre-treatment tumor tissues.

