### 4. Experimental Design and Methods

#### 4.1 Duration of Study

20 patients are planned to be enrolled. The patients will be under active treatment with cetuximab monotherapy for approximately 8 weeks. Afterwards, they will be assessed for disease response and determination of whether the lesion is potentially resectable will be made. We expect that patients will be accrued within 24 months and that followup time will average 18-24 months per patient.

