## 6. Study Parameters

Evaluations	Pre-cetuximab	Weekly during neoadjuvant cetuximab	Post-cetuximab (Week 9)	At surgery or prior to RT 	30 days after surgery or XRT	Follow ups every 3 months after surgery or XRT for 2 years	After locoregional or distant failure
History, physical exam and tumor site assessment	X  (within 14 days of treatment)	X 	X 		X 	X 	X 
Photo of tumor and/or rash at head, neck, upper torso put into EMR	X (within 14 days of treatment)	X 	X 				
Incisional/core biopsy of primary tumor and loco-regional lymph nodes if involved	X  (within 30 days of treatment)			X  (any time during this interval)			X (within 30 days of relapse)
Biopsy of skin	X  (within 30 days of treatment)			X  (any time during this interval)			X (within 30 days of relapse)
CBC, differential, platelets	X (within 14 days of treatment)	X			X	X	
Serum Chemistries 	X (within 14 days of treatment)	X	X	X	X	X	
Liver Enzymes 	X (within 14 days of treatment)	X			X	X	
Pregnancy Test 	X (within 14 days of treatment)						

Radiographic Assessments 	X  (within 30 days of treatment)		X 			X	X 
---------------------------------------	---	--	----------------	--	--	---	----------------

\*A +/- 2 day window is allowed for all study assessments indicated on this trial except treatment for which a +/- 1 day window is allowed.

1. To include toxicity assessment, ECOG performance status, weight
2. Includes: Electrolytes, including serum magnesium, potassium, Calcium, BUN, Creatinine, Glucose,
3. Includes: Total and Direct. Bilirubin, AST/ALT, Alkaline Phosphatase, Albumin, Total Protein.
4. Women 18-55 who have not undergone menopause must have urine pregnancy test within 14 days of enrollment.
5. Tumor assessments as indicated by investigator, i.e. PET/CT, CT neck, chest/abdomen and pelvis or MRI of neck as needed to be obtained no more than 1 month prior to cetuximab; then per standard of care, in general, every three months after conclusion of surgery or XRT.
6. Every 7 days
7. Includes evaluation by surgery and radiation oncology for optimal local therapy. Surgery will assess optimal timing of rebiopsy during their evaluation of patient once neoadjuvant therapy is complete.
8. See section 11

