### 7.2.4 Repeat Bx after neoadjuvant cetuximab.

After 8 weeks of neoadjuvant cetuximab, tissue will either be harvested at surgery, or if the patient is not a surgical candidate, a biopsy specimen (preferably a core biopsy as opposed to a FNA) will be procured from the primary site or accessible lymph node. As

this tissue will be used for DNA and RNA sequencing, tissue that is fresh and sufficient in quantity is required. These specimens will be flash frozen and brought that same day to the BRS.

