## **11.2 Tissue to be collected**

All patients must have a diagnosis of squamous cell carcinoma (SCC) of skin prior to entering into this protocol. This diagnosis is typically achieved by a biopsy from either the primary site or FNA from a neck lymph node. However, the scant amount of tissue obtainable from an FNA would not be adequate for the molecular biology aspect of this protocol, which include

1. Providing tissue to the pathology department so that they are able to confirm diagnosis of SCC in the tissue retrieved, which then will be sent to FoundationOne™ for DNA sequencing and analysis of genetic mutations.
2. Providing frozen tumor to the Cancer Institute Functional Genomics Facility for RNA sequencing
3. Providing frozen tumor and skin tissue to be used in Western Blot analysis.
4. Providing FFPE tumor and skin tissue for use in IHC analysis.

Thus, all patients on the protocol, prior to neoadjuvant cetuximab, will have an incisional/core biopsy from the primary site and a skin punch biopsy even though they already have a diagnosis of SCC. Incisional biopsy is favored over other types (core biopsy) for this biopsy because incisional biopsy has the best chance of supplying an adequate tumor sample.

After neoadjuvant cetuximab, additional tissue will be obtained at surgery or if the patient is not a candidate for surgery, biopsy will be obtained prior to treatment with XRT or with further systemic therapy. This tissue will only be used for RNA sequencing (and not sent to FoundationOne™ for DNA analysis), and thus a core biopsy may be employed here instead of incisional biopsy. A skin punch skin biopsy will also be performed after neoadjuvant cetuximab, preferably from a similar location as the first skin biopsy i.e. obtain two skin biopsies of neck and neck or right upper chest and right upper chest. If there is a locoregional/distant recurrence or persistence, a third incisional biopsy of locoregional/distant disease if possible and again paraffin-embedded sample will be sent to FoundationOne™ for analysis and fresh tissue may be obtained for RNA sequencing.

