## **15. Statistical Considerations**

### **15.1 Primary Hypothesis**

We hypothesize that the response rate to cetuximab is greater than 10%.

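### Post-treatment specimen type partly follows response, so the shrinkage and caspase-3 association is partly confounded with how the tissue was obtained, and section 15.5 does not allow for it

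*Combined protocol and SAP*

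**What the plan says.** All places are in the combined protocol and SAP.

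- **Source of post-treatment tissue.** Section 1.2 (molecular correlates): "Patients will also have tissue harvested at surgery that will undergo molecular analysis, or a second post treatment biopsy if surgery is not feasible". Section 7.2.4 agrees: "tissue will either be harvested at surgery, or if the patient is not a surgical candidate, a biopsy specimen", with a core preferred to an FNA. Section 11.2 adds for this time point that "a core biopsy may be employed here instead of incisional biopsy". At baseline, section 11.2 favours an incisional biopsy.
- **Link between surgery and response.** Section 1: "patients may be able to go on to surgical resection if adequate disease response is achieved". Section 4.1 places the decision on resectability after the response assessment.
- **Marker objectives.** Section 1.2: "Determine if tumor shrinkage with cetuximab is associated with increased apoptosis as evidenced by activated caspase-3", using pre- and post-treatment tissue. ADCC is a post versus pre comparison (section 1.2), and so is RNA sequencing (section 11.1).
- **Schedule.** Section 6 has a row "Incisional/core biopsy of primary tumor and loco-regional lymph nodes if involved", marked in the column for surgery or before radiotherapy. It may be done at any time in that interval, and note 7 leaves the timing of rebiopsy to the surgeons.
- **Analysis.** Section 15.5 offers a chi-square test, a two-sample t-test or a correlation, according to variable type. Neither the tissue sections nor section 15.5 mentions specimen type as something to adjust for or stratify by.

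**The concern.** Shrinkage helps to decide who has surgery. Surgery decides how the post-treatment sample is obtained, and that sample supplies the marker that is then related to shrinkage. If resected tissue and biopsy tissue read differently on caspase-3 for reasons unrelated to the drug, the difference falls mainly on the high-shrinkage side. It could create the association the objective looks for, or hide a real one. Time since the last dose may differ in the same way, because rebiopsy timing is not fixed.

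Section 2.1 presents the serial biopsies as a main strength and intends them to suggest predictors for later trials. If the specimens are not labelled by type, the analysis cannot separate the two explanations afterwards.

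**Working it through.** **1. The plan's own figure.** Section 4.1: "20 patients are planned to be enrolled". Section 15.2 uses an exact one-sided binomial test with a null rate of 10% and an expected rate of 30%. Rejecting at 5 or more responses gives P(X ≥ 5 | 20, 0.10) = 0.0432 and P(X ≥ 5 | 20, 0.30) = 0.7625. The stated 4.32% and 76.2% are reproduced. They concern the primary endpoint only. The expected rate gives 0.30 × 20 = 6 responders and 14 non-responders for the marker comparison.

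**2. Size of a spurious difference.** Let a and b be the proportions of responders and non-responders who are resected, and let s be the shift in SD units that resected tissue adds to the marker. With no true link, the expected difference between responders and non-responders is s × (a − b). The documents give none of a, b or s, so all three are assumptions.

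| a vs b | s × (a − b) at s = 1.0 | t-test false positives, s = 0.5 | s = 1.0 |
|---|---|---|---|
| 100% vs 0% | 1.0 × 1.0 = 1.00 SD | 16% | 46% |
| 90% vs 20% | 1.0 × 0.7 = 0.70 SD | 10% | 25% |
| 80% vs 40% | 1.0 × 0.4 = 0.40 SD | 7% | 11% |
| 60% vs 60% | 1.0 × 0 = 0 SD | 5% | 5% |

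The rates are from simulation (6,000 runs per setting, n = 20, each patient a responder with probability 30%). The two-sided 5% level is assumed, because section 15.5 states none for these tests. At 100% vs 0%, response and specimen type are the same variable, and no adjusted responder comparison can be made.

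**3. Shrinkage as a continuous variable.** This is closest to the objective as worded. Shrinkage is N(0,1), response is the top 30%, and marker change = s × surgery + N(0,1). With s = 1.0:

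| a vs b | Correlation, false positives |
|---|---|
| 100% vs 10% | about 22% |
| 100% vs 30% | about 16% |
| 100% vs 50% | about 9% |
| 80% vs 40% | about 8% |
| 100% vs 70% | about 6% |
| 80% vs 60% | about 5.5% |

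With s = 0.5, a = 100% and b from 10% to 50%, the range is about 6-10%.

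**4. Effect of adjustment.** The partial correlation given specimen type returns the false-positive rate to about 5% (5.2% and 5.8% in two runs at 100% vs 30%, s = 1.0). The price is power. For a true slope of 0.7 SD per SD and no specimen effect, power falls from about 79% unadjusted to about 55-73%, depending on the resection pattern.

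**5. ADCC and RNA.** These are compared post versus pre, not by shrinkage. Setting section 11.2's baseline preference (incisional) beside its post-treatment sources (resected tissue, or possibly a core) shows that specimen type can change between a patient's two samples. A pre/post change then mixes drug effect with specimen effect, by a route that does not pass through response.

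**The case against.** The strongest reply is that the overlap may be small. Section 5.1.1 does not require unresectable disease, and a tumor of 2 cm or more is among its listed criteria. Section 1 calls the disease potentially resectable, section 2.1 speaks of shrinking tumors before surgery, and note 7 in section 6 has surgery and radiation oncology choose local therapy together. Non-responders may well be resected, and if 60-70% of them are, the inflation nearly disappears. This stands, and it is why the confounding is described as partial.

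It is also fair to say that the documents give no evidence of a specimen effect on caspase-3; its existence, size and direction are assumed. Section 7.2.4 has specimens of both kinds frozen and delivered the same day, which reduces handling differences for frozen tissue. It says less about caspase-3, which section 11.1 assigns to immunohistochemistry on paraffin-embedded tissue.

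A reader might infer three stronger claims, which the documents do not support:

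- **A clean split, with shrinking tumors resected and all others cored.** Section 1 says only that patients may go on to resection, and a core is preferred or permitted, not required.
- **A false-positive rate near one half.** Comparing the marker by resected versus not resected does give 49-55% at a 1 SD shift with all responders resected. The plan names no such test: conversion to resectability is related to FoundationOne mutations (sections 1.2 and 2.1).
- **The same response-driven bias in ADCC and RNA.** Those comparisons are post versus pre.

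Finally, these are goals to explore in a 20-patient pilot, and section 17 makes much of the laboratory work depend on funds. That limits the weight of the point but does not remove it.

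**Conclusion.** The concern holds in a limited form. Specimen type follows surgical candidacy, candidacy depends at least partly on response, and section 15.5 has no means of separating specimen type from shrinkage in the caspase-3 objective. Under an assumed 1 SD specimen effect, the correlation's false-positive rate lies between about 5-6% and about 22%, according to how differently responders and non-responders are resected. With no specimen effect, or with surgery unrelated to response, there is no bias. For ADCC and RNA the issue is the within-patient change of specimen type, and the documents allow no estimate of its size.

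The primary response-rate test is untouched. The change is worth considering because it is cheap, not because the trial's main conclusion is at risk.

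**What to change.** 1. Record for each post-treatment sample the specimen type (resected tissue, incisional, core) and the time since the last cetuximab dose.
2. In section 15.5, report the association of shrinkage with caspase-3 change both unadjusted and adjusted for specimen type, or displayed by specimen type. State in advance that it will be called uninterpretable if specimen type and response coincide.
3. Report ADCC and RNA pre/post changes by specimen type.
4. Reconcile sections 1.2, 7.2.4 and 11.2 with the biopsy row in section 6, so that sites know whether the post-treatment sample in surgical patients is resected tissue or a biopsy. At the same time, reconcile section 11.2, which limits post-treatment tissue to RNA sequencing, with sections 1.2 and 11.1, which need it for caspase-3 and ADCC.

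The cost is one or two data fields, a few sentences and little analysis work. No added biopsy is asked for: a separate sample from the tumor in place at operation would be an extra procedure and would still leave anaesthesia different between the groups. The downside is the loss of power shown above, so the adjusted result should stand beside the unadjusted one and not replace it.

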## **2. Background and Significance**

### **2.1 Supporting Data and Rationale**

Nonmelanoma skin cancers are the most common malignancies among Caucasians. Squamous cell carcinoma (SCC) of the skin is an increasingly common diagnosis, and is the second most common type of skin cancer worldwide (Alam and Ratner 2001). Specifically, results from a population based study performed in the United States using governmental data on skin cancer procedures and related office visits estimated the number of new skin cancer diagnoses to be over

3.5 million in 2006 (Rogers, Weinstock et al. 2010). Regardless of the true incidence, it is known that the number of cases has consistently risen over the past 20 years. This observation can be related to improved detection of skin cancer, increased UV and tanning bed exposure, and the aging of the U.S. population, since the incidence of SCCS increases dramatically with age (Bauman, Eaton et al. 2007). It follows, then, that with a 10% decrease in stratospheric ozone annually and the continued growth of the aging U.S. population, the number of metastatic squamous cancers arising from a skin primary is certain to continue increasing annually for the foreseeable future. These cancers also plague patients who are recipients of solid organ transplants, historically a difficult population of patients for the delivery of cytotoxic systemic therapies.

[figure not shown]
[figure not shown]
It should be noted that SCC and its precursor lesions can carry a significant morbidity associated with diagnosis, with an opportunity for recurrence, local or distant metastases, treatment related complications, and increased risk for development of secondary cancers (Wassberg, Thorn et al. 1999). Most often, these lesions are localized and amenable to surgery. Larger and more invasive lesions often require multimodality care, but relatively little has been done to investigate a generalized management plan for these situations (Gaffney, Soyer et al. 2013). As a result, there is a lack of high-level data on systemic treatment options for cutaneous SCC unamenable to resection. A 10-year cohort study involving 985 patients with SCC found a 3.7% risk of metastasis and 2.1% risk of disease-specific death (Schmults, Karia et al. 2013). Published case reports have demonstrated responses with platinum-based chemotherapy with occasional complete responses noted in this patient population (Lawson, Otto et al. 2008, Nakamura, Okuyama et al. 2013). There are no prospective phase III studies available, and only one prospective phase II study regarding the use of platinum-based chemotherapy in this population. Cisplatin, either as a single agent or combined with 5-FU, has occasionally produced useful responses, but again, data supporting efficacy is limited. In the only phase II study of biochemotherapy with interferon alfa, cis-retinoic acid and cisplatin, 35 patients were assessed for response, 11 of which had distant metastases (Shin, Glisson et al. 2002). One of the 11 patients experienced a complete response. Twelve patients with only regional lymph node metastases were treated and 3 had either a partial (2) or complete (1) response. This lends some credence to a cisplatin-based regimen. Other studies are retrospective and most are anecdotal (Weinberg, Ogle et al. 2007, Cranmer, Engelhardt et al. 2010). In summary, historically, advanced SCCS is incredibly challenging to treat given its presence in a patient population which often has multiple comorbidities. In addition, the absence of randomized clinical trials that would provide guidelines for therapy further complicates this clinical situation. **These facts underscore that this population of patients represents an unmet medical need that is likely to grow as the elderly U.S. patient population increases and as such, is a ripe area for clinical investigation.**

One potential novel treatment option includes targeting the epidermal growth factor receptor which is highly expressed in many epithelial tumors, including squamous cell carcinomas of the skin (DeConti 2012). The epidermal growth factor receptor (EGFR) has also been implicated in SCC development, specifically, it has been shown to be involved in UV-induced skin carcinogenesis (Gaffney, Soyer et al. 2013). Additional evidence in support of a relevant role of EGFR expression in these cancers includes a retrospective study, which demonstrated that primary cutaneous SCC of the head and neck that subsequently metastasized were more likely to overexpress EGFR than those

that did not (Bonner, Harari et al. 2006). Accordingly, the development of anti-EGFR drugs has been pursued for use in various malignancies.

One such new EGFR-directed therapy is cetuximab, a monoclonal antibody that competitively inhibits EGFR (Gaffney, Soyer et al. 2013). Its mechanism of action is likely dual, in that it competitively inhibits natural EGFR ligands, preventing EGFR phosphorylation and it elicits antibody-dependent cell cytotoxicity (ADCC) (Fan, Masui et al. 1993, Lopez-Albaitero and Ferris 2007). It has been approved in the treatment of SCC of the head and neck, in combination with radiation and/or platinum-based chemotherapy (Gaffney, Soyer et al. 2013). A randomized controlled trial by Bonner et al. in advanced oropharynx, hypopharynx, and larynx SCC of external beam radiation therapy + cetuximab versus EBRT alone revealed an improvement in 5 year overall survival for the cetuximab arm from 36.4% to 45.6% (Bonner, Harari et al. 2006). Cetuximab has also been used in EGFR-expressing, KRAS wild-type metastatic colorectal cancers in combination with chemotherapy regimens (Gaffney, Soyer et al. 2013). Additionally, studies demonstrating the efficacy of Cetuximab in recurrent squamous cell carcinomas have been promising (Bauman, Eaton et al. 2007). Data regarding use of cetuximab in advanced SCCS is scarce and consists of a few case series reports and one phase II trial (Nadiminti, Shao et al. 2013). The largest of these studies was published by Maubec et al, who reported the use of cetuximab as first line therapy for unresectable squamous cell carcinoma of the skin expressing EGFR in a phase II nonrandomized setting. The trial accrued 36 poor-prognosis patients and demonstrated an overall disease control rate of 69% (Maubec, Petrow et al. 2011). Additionally, a prospective study looking at cetuximab with or without systemic chemotherapy in patients with locally recurrent or unresectable disease demonstrated clinical improvement in pain, tumor ulcer, and bleeding compared to pretreatment symptoms. Treatment with cetuximab was generally well tolerated with the main side effect being skin rash (Nadiminti, Shao et al. 2013). Multiple published case and retrospective reports have documented tumor responses in patients with SCCS treated with cetuximab (Bauman, Eaton et al. 2007, Suen, Bressler et al. 2007, Miller, Sherman et al. 2010, Kim, Eleff et al. 2011, Kalapurakal, Malone et al. 2012), with one from our institution demonstrating an impressive complete response in an elderly patient with squamous disease (Kim, Eleff et al. 2011) (Figure 1).

